10.1 Actions to be taken in the case of an adverse event

When an adverse event is recognized, the principal investigator or sub-investigator shall immediately take appropriate measures and record the event in the medical record and case report form without any discrepancy. In addition, when food intake is discontinued or treatment for an adverse event becomes necessary, research participants should be informed.

To identify the food during an emergency evaluation, the principal investigator will ask the person in charge of allocation to disclose the results by opening the package for the case in question.

10.2 Reporting of serious adverse events

If the principal investigator recognizes the occurrence of a serious adverse event, it should be promptly reported to the hospital through the Clinical Research Support Center, and the hospital director shall request the Ethics Committee to deliberate on whether or not to continue the trial. The principal investigator shall share information on the occurrence of the adverse event with the sub-investigators involved in the research.

A first report (emergency report) and a second report (detailed report) shall be made.

10.3 Other adverse events

Other adverse events are recorded in case report forms, according to the procedures described in 8 (Confirmation of adverse events and side effects).

11. Compliance with the research protocol and handling of deviations from it

11.1 Compliance with the research protocol

The principal investigator and sub-investigators will conduct the trial in compliance with the research protocol.

11.2 Handling of deviations from the research protocol

The principal investigator or sub-investigator shall not deviate from or change the research protocol before obtaining approval by the hospital director and prior review by the Ethics Committee.

The principal investigator or sub-investigator may deviate from or change the research protocol for unavoidable reasons such as emergency avoidance, prior to approval by the Ethics Committee. In such cases, the principal investigator or sub-investigator shall promptly submit to the Ethics Committee the details of the deviation or change, the reasons for the deviation or change, and a draft of the revised research protocol, if necessary, for approval by the Ethics Committee and the hospital director.

If there is any deviation from the research protocol, the principal investigator or sub-investigator shall record all deviations, together with the underlying reasons.

If the principal investigator or sub-investigator realizes that this clinical research does not comply with ethical guidelines for medical research on human participants (only in cases where the degree of non-compliance is serious), approval from the hospital

director will be requested. The hospital director shall request the Ethics Committee to deliberate on whether or not to continue the trial, take the necessary measures, and then cooperate with the hospital director in reporting and publicizing the status and results of the measures to the Minister of Health, Labor, and Welfare.

12. Renewal, termination, discontinuation, and suspension of research

12.1 Renewal and termination of research

The principal investigator shall report the status of the research to the hospital director once a year (in January), and the hospital director shall request the Ethics Committee to discuss the status report.

12.2 Discontinuation or suspension of research

The principal investigator will consider whether or not to continue the trial if any of the following items applies:

- 1) Critical information on the quality, safety, or efficacy of the food intake is obtained.
- 2) The Ethics Committee instructs changes to the implementation plan, and it is judged to be difficult to accept these changes.
- 3) The hospital director recommends or instructs discontinuation based on the opinion of the Ethics Committee or the Effectiveness and Safety Evaluation Committee.

When the decision to discontinue or suspend the research is made, the decision shall be promptly reported to the hospital director in writing, together with the reasons for the decision.

13. Research implementation period

From approval by the Ethics Committee until December 31, 2023.

Registration period: from approval by the Ethics Committee until December 31, 2019.

14. Statistical matters

14.1 Target number of cases and rationale for setting the target

The null hypothesis posits that there is no change in SMI between the NMN intake group and the placebo intake group. Based on existing published evidence⁵, we assumed that the standard deviation for SMI in healthy participants was 0.60 kg/m² and that the expected change in SMI due to food intake was 0.45 kg/m²*. In this case, the sample size that would allow us to reject the above null hypothesis with a 95% confidence interval would be 20 samples for each group (40 samples in total) using calculations based on Cancer Research and Biostatistics. The predicted dropout rate was 5%, and the study was started with 42 participants (21 participants in each group).

*We expect a change of 6–7% based on pre-studies^{6,7}. Given a baseline value for muscle mass loss in the elderly of 6.75 kg/m² for men⁸, the cutoff value for the amount of NMN that could improve muscle mass loss associated with aging was calculated to be $6.75 \text{ kg/m}^2 \times 0.06 = 0.405 \text{ kg/m}^2$ and $6.75 \text{ kg/m}^2 \times 0.07 = 0.4725 \text{ kg/m}^2$. The cutoff value was 0.45 kg/m². Considering that SMI decreases with age, an increase in SMI of 0.45 kg/m² in men aged 70–74 years is equivalent to a rejuvenation of 10–20 years⁹.

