14.2 Analysis items and methods

Primary endpoint: change in SMI measured by BIA.

Change in SMI defined as SMI at week 12 - SMI at baseline, where SMI is calculated as limb muscle mass (kg) / height² (m²).

Each endpoint is a continuous quantity, and is based on data from a single time point.

The results of the analysis will be presented as the adjusted least square means ± standard error.

Subgroup analysis is performed with age and BMI as subgroups.

The incidence rate and 95% confidence interval will be presented for each adverse event.

1) Within-group comparison

Depending on the variability of the population, the corresponding *t*-test (paired *t*-test) or Wilcoxon signed-rank test will be used to compare the measurements before, 6 weeks after, and 12 weeks after intake. In cases where the aforementioned analysis methods do not apply, a statistical method more appropriate for aggregated data will be employed.

2) Between-group comparison

Depending on the variability of the population, the unpaired *t*-test or Mann–Whitney U test will be used to compare the measured values before, 6 weeks after intake, and 12 weeks after intake, and calculate the corresponding changes. The difference between pre-and post-intake values will be compared between groups. Analysis of covariance will be performed if the pre-intake values cannot be ignored as confounding. In addition, treatment comparison is performed using mixed model analysis. When endpoints cannot be calculated using mixed model analysis, endpoints follow mixed-effect model for repeated measures (MMRM). In other cases where the aforementioned analysis methods do not apply, a statistical method more appropriate for aggregated data will be employed.

3) Safety evaluation

Analysis will confirm the absence of any changes associated with the intake of test foods that would require medical attention.

4) Standards and software

Statistical analysis shall be conducted using a two-tailed test, and the significance level shall be set at 5%. Participants who do not comply with the study requirements, such as an intake rate of less than 90%, will be excluded from the analysis.

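### Section 14.1 justifies 20 per group by a confidence level and states no power; its own inputs give about 64% power under the planned two-sided test, if 0.60 is taken as the SD of the analysed change

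*Protocol*

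**What the plan says.** Protocol section 14.1 frames the trial as a comparison of two groups: "The null hypothesis posits that there is no change in SMI between the NMN intake group and the placebo intake group". It then gives two numerical inputs. For the SD, "we assumed that the standard deviation for SMI in healthy participants was 0.60" kg/m². For the effect, "the expected change in SMI due to food intake was 0.45" kg/m², which a footnote places between 0.405 and 0.4725 kg/m² (6% and 7% of 6.75). From these it concludes that "the sample size that would allow us to reject the above null hypothesis with a 95% confidence interval would be 20 samples for each group", and on dropout it adds "The predicted dropout rate was 5%, and the study was started with 42 participants (21 participants in each group". No power appears in the section.

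Section 14.2 fixes the rest of what a calculation needs. The endpoint is a change score: "Change in SMI defined as SMI at week 12 - SMI at baseline". The basic between-group test is an unpaired t-test or a Mann–Whitney test, with analysis of covariance and mixed models also named. On the error rate, "Statistical analysis shall be conducted using a two-tailed test, and the significance level shall be set at 5" percent.

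**The concern.** Section 14.1 reads as a completed sample-size calculation, but the quantity it uses to fix the size is a confidence level. That controls how often a true null is rejected. It does not say how often a real difference of 0.45 kg/m² would be found, so by itself it leads to no particular number of participants. With no power stated, the only check is to put the section's inputs into the test of section 14.2 and see what 20 per group provides.

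This is the only justification for the trial's size on its primary endpoint. A reader will take it to mean that a true difference of 0.45 kg/m² is likely to be detected. If the inputs do not support that, a non-significant result could be given more weight against such an effect than it deserves.

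**Working it through.** **Inputs.** Difference δ = 0.45 kg/m², footnote range 0.405 to 0.4725 (14.1). SD σ = 0.60 kg/m² (14.1). Two-sided α = 0.05 and unpaired t-test (14.2). n = 20 per group (14.1). Power: not stated.

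**Step 1: can 20 be reproduced?** The usual two-group formula is n per group = 2 × [(z for α + z for power) × σ/δ]², with σ/δ = 0.60/0.45 = 1.333.

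| Reading | n per group |
|---|---|
| Two-sided 5%, 80% power: 2 × [(1.960 + 0.842) × 1.333]² = 27.9 | 28 (29 by t-test) |
| Two-sided 5%, 90% power: 2 × [(1.960 + 1.282) × 1.333]² = 37.4 | 38 (39 by t-test) |
| One-sided 5%, 80% power | 22 (23 by t-test) |
| Two-sided 5%, 65% power | 20 |
| An observed 0.45 just excludes zero: 2 × (1.960 × 1.333)² = 13.7 | 14 |

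The two-sided two-group formula returns 20 only at a power of about 65%. The one-sided reading comes closest among conventional choices, but it conflicts with the two-tailed rule in 14.2 and still needs 22 or 23. The literal confidence-interval reading gives about 14, so it does not explain 20 either.

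**Step 2: what does 20 per group give?** The standard error of the difference is 0.60 × √(2/20) = 0.1897. The noncentrality is 0.45/0.1897 = 2.372. With 38 degrees of freedom the two-sided critical value is 2.024. From the noncentral t distribution:

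| True difference (kg/m²) | Power at 20 per group |
|---|---|
| 0.405 | 54.8% |
| 0.45 | 63.7% |
| 0.4725 | 68.0% |

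The normal approximation at 0.45 gives 66.0%. With all 21 per group evaluable, the t-test figure is 66.0%.

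**Step 3: detectable difference.** Solving the same noncentral t calculation for 80% power at 20 per group and SD 0.60 gives 0.545 kg/m², which is 0.545/6.75 = 8.1% of the baseline value in the footnote, against the 6–7% it expects.

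**Step 4: dependence on the SD.** Section 14.1 gives 0.60 as the SD of SMI, while 14.2 analyses change in SMI. If the SD is the same at both visits and ρ is the correlation between them, the SD of change is 0.60 × √(2(1 − ρ)). The protocol gives no ρ, so the values below are assumptions.

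| Assumed ρ | SD of change | Power at 20 per group for 0.45 |
|---|---|---|
| 0 | 0.85 | 37% |
| 0.5 | 0.60 | 64% |
| 0.7 | 0.46 | 85% |
| 0.9 | 0.27 | over 99% |

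The 64% therefore applies to the change score only if ρ = 0.5, that is, if 0.60 happens also to be the SD of change.

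**The case against.** The strongest reply is that no stated number is contradicted. The protocol sets no power target, so 64% falls short of nothing written down. If the observed difference were exactly 0.45 with SD 0.60, the 95% interval would have half-width 2.024 × 0.1897 = 0.38 and would exclude zero. The study is also described as exploratory (sections 1 and 6.2), and 42 participants may be all that was intended. The first part stands in that 14.1 misses no declared target. It does not rescue the sentence. An observed 0.45 is not a true 0.45, and the just-significant reading leads to about 14 per group rather than 20. Exploratory status can justify a small trial, but not a calculation that its own inputs do not support.

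A reader might infer more: that the trial is underpowered and would miss a true 0.45 kg/m² more than one time in three. The documents do not support that without a condition. It holds only if 0.60 is the SD of the quantity analysed. Under equal SDs at the two visits, a change-score t-test reaches 80% power once the correlation is about 0.66, and the protocol says nothing about where the correlation lies. Adjusting for baseline, which 14.2 names as a conditional option, would also alter the figure.

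Two further inferences should be left aside. One is that the dropout allowance is wrong: 21 × 0.95 = 19.95, which is 20 within rounding. The other is that a one-sample formula was used: the protocol shows no formula, so this would be a guess.

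**Conclusion.** The point holds as a defect in the stated justification. Section 14.1 uses a confidence level as the criterion for size and omits power, and its inputs do not give 20 per group at any conventional power under the test planned in 14.2. On those inputs the power is about 64% (55% to 68% over the footnote's range), and 80% power would need 29 per group, 9 more than stated.

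These figures assume an unpaired t-test, two-sided 5%, 20 evaluable per group, and 0.60 kg/m² as the SD of the analysed change. The arithmetic is firm and the last assumption is not. The document therefore cannot show whether the trial's actual power is poor or ample, which is itself a reason to state the power and its assumptions openly.

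**What to change.** Keep the planned 42 participants. In section 14.1, delete the 95% confidence interval as the size criterion and replace the sentence with wording such as:

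> Taking 0.60 kg/m² as the SD of the analysed change, 20 evaluable participants per group give 64% power to detect a difference of 0.45 kg/m² (two-sided 5%, unpaired t-test). The difference detectable with 80% power is 0.545 kg/m².

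Add directly after it that 0.60 is a cross-sectional SD of SMI, that power depends on the SD of the change from baseline to week 12, and that assumed correlations of 0, 0.5, 0.7 and 0.9 would give 37%, 64%, 85% and over 99%. When an SD of change can be justified from a source, replace both the 64% and the 0.545 with figures based on it.

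The cost is a few sentences in one section. No participants are added, and the endpoint and test stay as they are. On the inputs now stated the protocol will carry a less favourable figure, which a justified SD of change could move in either direction.

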6.5 Food dosage and administration period

Oral intake of 250 mg NMN or placebo for 12 weeks.

There have been several reports of NMN administration to mice via intraperitoneal or oral routes at doses of 100–500 mg/kg/day¹. In particular, in long-term experiments, whereby NMN was administered at doses of 100 or 300 mg/kg/day for 1 year, no significant adverse side effects were observed². Taking into account the absorption area of the small intestine, 100 mg/kg/day of NMN in mice is equivalent to 8 mg/kg/day of NMN in humans². In an oral acute toxicity test on rats conducted by Mitsubishi Corporation Life Sciences Limited. , no particular problems were observed at a dose of 2000 mg/kg/day. Even though there are no reports of NMN administration in humans, three clinical studies have been registered in Japan and one in the United States. The latter (ClinicalTrials.gov Identifier: NCT03151239) foresees a dose of 250 mg/day for 8 weeks, and one of the Japanese studies (UMIN Study ID UMIN000025739) envisions a dose of 100 or 200 mg/day for 24 weeks. In the case of NR, several clinical studies in humans have been reported, with doses of 100–2000 mg/day administered for up to 12 weeks causing no serious side effects⁴. In long-term NR administration experiments in mice, a dose of 400 mg/kg/day was administered for 12 weeks³. Based on the above experimental evidence, there is no significant difference between the effective dosage of NMN (100–300 mg/kg/day) and NR (400 mg/kg/day) in mice. The dose chosen in the present study was set in consideration of the doses used in the abovementioned clinical trials (100, 200, and 250 mg/day).

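### The 5% allowance behind 42 enrolled men covers dropout only, while 14.2 also excludes non-compliant men, so the expected analysed number falls below the stated 20 per group

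*Protocol*

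**What the plan says.** For variability, Protocol section 14.1 assumes: "the standard deviation for SMI in healthy participants was 0.60 kg/m²". For the effect size it supposes: "the expected change in SMI due to food intake was 0.45 kg/m²". From these it concludes that the number needed "would be 20 samples for each group (40 samples in total"). It then moves from the required to the enrolled number: "The predicted dropout rate was 5%, and the study was started with 42 participants (21 participants in each group"). Dropout is the only loss named there, and the term is not defined.

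Section 14.2, item 4 (Standards and software), sets a two-sided 5% test and adds an exclusion: "Participants who do not comply with the study requirements, such as an intake rate of less than 90%, will be excluded from the analysis". No expected rate is attached to it, and the sentence does not limit it to a secondary or per-protocol analysis.

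Section 9 lists the grounds for discontinuation. Low intake is not named among them.

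**The concern.** The two sections describe different losses. A man can attend every visit, provide a week-12 SMI and still be removed under 14.2 because he took too few doses. He is not a dropout in the ordinary sense, and section 9 does not name low intake as a reason to discontinue him. The enrolled number, however, was inflated for dropout alone.

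At stake is whether the size on which 14.1 rests its case for rejecting the null hypothesis is the size that the analysis will have. If the 14.2 rule removes anyone, the comparison is expected to rest on fewer than 20 per group, and a reader who takes 20 from 14.1 will overrate its power and precision.

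**Working it through.** **Inputs.** From 14.1: 20 per group required, 5% dropout, 21 per group enrolled, difference 0.45 kg/m², SD 0.60 kg/m². From 14.2: two-sided test at 5%, and exclusion below 90% intake or for other non-compliance. From 6.5: 12 weeks of intake. The share c of completers excluded under 14.2 is not in the protocol and is assumed here.

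**Step 1: reproduce the plan's figure.** 40 x 1.05 = 42, the enrolled number. Dividing by retention gives 40/0.95 = 42.1, or 20/0.95 = 21.05 per group. With 21 enrolled per group, 21 x 0.95 = 19.95 are expected to remain. The stated 42 is reproduced, and dropout alone is covered to within 0.05 of a man per group.

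**Step 2: what the 90% rule means.** Counting intake in days, 12 x 7 = 84. Eight missed days give 76/84 = 90.5%, which passes. Nine give 75/84 = 89.3%, which is excluded.

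**Step 3: add the second loss.** Retention = 0.95 x (1 - c), and the expected analysed number per group = 21 x retention. Since 21 x 0.95 is already 19.95, no value of c above zero leaves an expected 20.

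**Step 4: power and precision at the rounded n per group.** The noncentrality of the two-sample t-test is 0.45 / (0.60 x √(2/n)) = 0.75 x √(n/2). The 95% half-width is t(0.975, 2n - 2) x 0.60 x √(2/n). For n = 20 this is 2.024 x 0.1897 = 0.384 kg/m².

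| c (assumed) | Retention | Expected per group | n used | Noncentrality | Two-sided power | Half-width, kg/m² |
|---|---|---|---|---|---|---|
| 0% | 0.9500 | 19.95 | 20 | 2.372 | 63.7% | 0.384 |
| 5% | 0.9025 | 18.95 | 19 | 2.312 | 61.4% | 0.395 |
| 10% | 0.8550 | 17.96 | 18 | 2.250 | 58.9% | 0.406 |
| 15% | 0.8075 | 16.96 | 17 | 2.187 | 56.4% | 0.419 |

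**Limits of the table.** The same loss is assumed in both groups. The value 0.60 is described in 14.1 as the SD of SMI, whereas the primary endpoint is the change in SMI. The power and half-width columns therefore hold only if the SD of change equals 0.60. The expected-number column does not depend on the SD.

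**The case against.** The best defence is that 14.1 does not define dropout. If the authors meant every loss from the evaluable sample, the two sections agree. This is possible, but 14.1 does not say so, and section 9 does not treat low intake as a reason to leave the study. At the least a clarifying sentence is needed.

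A second objection is that non-compliance may be rare. Under 6.9 a forgotten intake may be made up later the same day, section 7.6 has intake recorded daily, and eight missed days still pass. With no rate in the protocol, the true loss could be near zero. This stands, and it is why the rates above are a range of assumptions with 0% included.

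Third, the consequence is small. It costs about 2 to 7 points of power, from a base that is already only about 64%. The normal approximation at the same inputs gives 28 per group for 80% two-sided power. That base is a separate and larger matter. The trial is also labelled exploratory. Both remarks are fair on weight, but 14.1 still justifies its number by the ability to "reject the above null hypothesis with a 95% confidence interval", so the number should match the planned analysis.

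A reader might infer that 42 is itself a calculation error because 40/0.95 exceeds 42. The documents do not support this. The gap is 0.05 of a man per group, and an allowance of this kind aims at the expected number, not at a guarantee for each arm.

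**Conclusion.** The inconsistency is real and of modest size. The 5% allowance in 14.1 is fully used by dropout, and the exclusion in 14.2 is not counted. For any non-zero exclusion rate, the 42 enrolled men are expected to leave fewer than 20 per group in the analysis. That conclusion rests on reading dropout in its ordinary sense and on the 14.2 exclusion applying to the primary comparison, as its wording indicates.

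The size rests on an assumed rate. With 5% to 15% of completers excluded, about 19 to 17 per group remain, against 20 stated. Power is then 61% to 56% instead of 64%, and the half-width 0.39 to 0.42 instead of 0.38 kg/m², conditional on 0.60 being the SD of change.

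A reader might go further and infer that the trial will certainly fall well short of 20, or that a stated power is wrong. Neither follows: the protocol gives no non-compliance rate, and 14.1 states no power, only a 95% confidence interval.

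**What to change.** Make 14.1 and 14.2 agree, without enrolling more. Either of two changes is enough.

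- **Count both losses.** Restate in 14.1 the expected analysed number per group after dropout and the 14.2 exclusions, using a combined loss rate that the study team states and justifies itself. Give the power or confidence interval width at that number, and say whether the 0.60 is meant as the SD of the change. The rates used above are illustrations and should not be adopted by default.
- **Remove the second loss.** Keep all randomised men with a week-12 SMI in the primary analysis, use the 90% rule only for a sensitivity analysis, and let 14.1 count dropout only.

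The first costs a less favourable figure in the sample size rationale. The second costs a change to one sentence in 14.2 and brings men with low intake into the primary comparison. Neither changes enrolment or visits.
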